## Brief Summary/Abstract

The primary objective of this study is to investigate the effectiveness of local antibiotic versus placebo in the prevention of infections in open fractures. The study will assess whether local treatment of open fractures with the antibiotic tobramycin (in addition to standard systemic antibiotics) will decrease the risk and rate of infection, time to fracture union, and rate of re-operation. This will be studied using a randomized controlled clinical trial design in adult population of age 18-70 years who present with open fractures. About 133 subjects will be recruited in this study at UVA. There will also be similar studies performed at University of Florida- Jacksonville and Medical University of South Carolina and we will be performing a collaborative site analysis study with those centers and we will be sharing demographic, infection and treatment information (at either 2 or 6 weeks), and any adverse events that occur.

**Note:** Standard protocols at UVA will be followed for systemic antibiotic administration. No specimens will be collected for research purposes. The patient will otherwise receive the standard of care treatment for their fractures.

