#### **Subjects- see below**

- 1. Provide target # of subjects (at all sites) needed to complete protocol.** 133
- 2. Describe expected rate of screen failure/ dropouts/withdrawals from all sites.**

Approximately, 20% of subjects will be lost to follow up

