**3. How many subjects will be enrolled at all sites? 133**

**4. How many subjects will sign a consent form under this UVa protocol? 133**

**5. Provide an estimated time line for the study. 2 years**

### **Inclusion/Exclusion Criteria**

**1. List the criteria for inclusion**

- Ages 18 – 70 years
- Gustilo Type I,II,IIa open fracture (s)
- Ability to provide informed consent (or proxy consent in cases where subject is temporarily impaired when intubated and sedated)
- Subject should be able to follow up at the scheduled times following surgery
- Subjects who may have compartment syndrome, renal insufficiency, and those who are immunosuppressed regardless of antibiotic administration will also be included in the study
- 

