**3. Provide a justification for the sample size used in this protocol.**

A sample size analysis was completed for different alpha and power levels. A one-sided test for proportions was chosen to compare the baseline (no treatment) group to the hypothesized proportion (treatment group); based on historical data, we assumed that the no treatment group would have a 10% infection rate, and the treatment group would have a 1% infection rate. Using an alpha of 0.05 and power of 70%, we would need to have 60 patients in each group.

With an expected accrual rate of 65 patients per year, we would expect to enroll 130 patients in two years. In order to maintain the sample size needed to ensure statistically valid results, we would want to enroll approximately 133 patients over the study period to end up with at least 120 patients in the analysis.

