**6. Have you been working with a statistician in designing this protocol? Yes**

IF YES, what is their name? [name]

Will data from multiple sites be combined during analysis? Yes

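### 133 is given both as the UVA enrolment and as the total at all sites, while data from other centres are to be combined, so the plan does not say which data set the 120-patient, 70%-power calculation covers

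*Combined protocol and SAP*

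**What the plan says.** - **Brief Summary/Abstract:** "About 133 subjects will be recruited in this study at UVA". It continues: "There will also be similar studies performed at University of Florida- Jacksonville and Medical University of South Carolina", with a collaborative analysis across the centres.
- **Subjects, item 1:** "Provide target # of subjects (at all sites) needed to complete protocol"; the answer is 133.
- **Subjects, items 3 and 4:** "How many subjects will be enrolled at all sites? 133" and "How many subjects will sign a consent form under this UVa protocol? 133".
- **Statistical Considerations, item 3:** "Using an alpha of 0.05 and power of 70%, we would need to have 60 patients in each group". It aims to enrol about 133 so that at least 120 are analysed, on an accrual of 65 patients a year. Item 2 gives 60 to 65 a year as UVA's own historical volume.
- **Statistical Considerations, after item 6:** "Will data from multiple sites be combined during analysis? Yes". Item 4 of the Data and Safety Monitoring Plan adds that spreadsheets from the other institutions will be merged with UVA's.
- **Statistical Considerations, items 4 and 5:** one one-sided test for proportions, and no analysis other than the primary one.
- **Statistical Considerations, item 1:** the other sites run their own randomisation, without UVA oversight.

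**The concern.** Read literally, UVA supplies all 133 of the 133 patients at all sites. That leaves none for two centres whose data will be combined with UVA's. The enrolment labels and the statement on combining data cannot all describe the same analysis.

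The practical question is which patients enter the primary test. The plan has one test, one power figure and two candidate data sets, and it does not link them. The Privacy Plan's closing paragraph has the pharmacy release the allocation once enough patients have been gathered, without saying how many or from which sites. If the choice of data set is still open when the allocation becomes known, the 5% one-sided error rate is no longer assured. A reader of the eventual report also could not tell whether the planned size had been reached.

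**Working it through.** **1. The plan's own figure.** Inputs from Statistical Considerations, items 2 and 3: p1 = 0.10, p2 = 0.01, one-sided alpha 0.05, power 70%, equal groups. The mean rate is 0.055.

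n per group = [z(0.95)·√(2·0.055·0.945) + z(0.70)·√(0.10·0.90 + 0.01·0.99)]² / 0.09²
= [1.645·0.3224 + 0.524·0.3161]² / 0.0081 = 59.8, rounded up to 60.

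Power at 60 per group = Φ[(0.09·√60 − 1.645·0.3224) / 0.3161] = Φ(0.528) = 70.1%. The stated figure reproduces.

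**2. Which patients that figure describes.** 65 a year for two years is 130, close to 133, and 65 is the top of UVA's own range. The calculation thus describes UVA patients. It would also fit an all-site total of 133. It does not fit 133 at UVA plus further patients.

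**3. Patients left for the other centres on the literal reading.** 133 (all sites) − 133 (UVA) = 0.

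**4. Power if other centres are added to 133 at UVA.** The documents give no number for the other centres, so the pooled totals below are assumptions. The formula is that of step 1. The 20% loss is from Subjects, item 2; about 10% is what going from 133 to 120 implies (120/133 = 90.2%). Numbers per arm are rounded down.

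| Assumed pooled enrolment | Per arm, 20% loss | Power | Per arm, 10% loss | Power |
|---|---|---|---|---|
| 200 | 80 | 80.8% | 90 | 84.7% |
| 266 | 106 | 89.5% | 119 | 92.3% |
| 399 (133 at each of three centres) | 159 | 97.2% | 179 | 98.3% |

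**5. False-positive rate if either test could be reported.** With no treatment effect and equal loss across sites, the UVA-only and pooled test statistics have correlation ρ = √(133/N). The chance that at least one exceeds 1.645 is 1 − Φ₂(1.645, 1.645; ρ), where Φ₂ is the bivariate normal distribution function.

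| N | ρ | Rate |
|---|---|---|
| 200 | 0.816 | 7.4% |
| 266 | 0.707 | 8.0% |
| 399 | 0.577 | 8.5% |

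**The case against.** The best defence is that this is not one three-centre trial. Section 5.1 of the Data and Safety Monitoring Plan describes collaborative site analysis studies as having no common protocol, and UVA does not oversee the other centres. On that view, all sites in the Subjects items means the sites under this protocol, that is, UVA alone. The Abstract, the Subjects items and the accrual basis then agree on 133.

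This reading is possible but strained, because Statistical Considerations uses the word sites for the other centres, both on randomisation and on combining data. Even if it is accepted, the combined analysis still has no sample size, no power and no stated status. Item 5 leaves no secondary place for it.

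A reader might go further and infer that the 70% power is itself contradictory. The documents do not support that: only one power figure is given, and it reproduces. A reader might also apply the stated 20% loss to 133, get about 106 analysed and 65% to 66% power, and count that against the plan here. That fall comes from a separate discrepancy between 20% loss and the roughly 10% built into the step from 133 to 120. It would exist with a single site.

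Two further objections stand. No section describes a separate UVA-only test, so the error inflation shows what the wording permits and not what anyone intends. Parts of the sections on outside institutions are also not in the text available for this review, so an outside-site number may have been stated there.

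**Conclusion.** The point holds as an inconsistency in labelling that leaves the primary analysis set undefined. With 120 analysed at UVA, power is 70%, as stated. For assumed pooled enrolments of 200 to 399 with 20% loss it would be about 81% to 97%, so pooling would raise power. The harm is that the stated size and power are not tied to a data set. An open choice between the two tests would put the one-sided error at about 7.4% to 8.5%.

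These figures rest on the plan's rates of 10% and 1%, its large-sample formula, equal groups, the assumed pooled totals and, for the error rate, a normal approximation. The plan does not name the version of the test, and exact power would depend on it.

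**What to change.** Before the treatment code is released:

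- Name one primary analysis set and tie the 120-patient, 70% figure to it. UVA-only matches the accrual basis of Statistical Considerations, item 3. If the sponsor prefers the pooled set, item 3 needs an all-site number and a new power figure.
- Make the other analysis a named secondary or supportive one.
- Stratify any pooled comparison by site, because each site manages its own randomisation.
- Give the UVA and all-site numbers separately in the Abstract and in the Subjects items.
- Amend Statistical Considerations, items 3 and 5, and the answer on combining data after item 6, to match.

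The cost is wording in these places, with no extra patients for a UVA-only primary analysis. The analysis not chosen loses primary status. The discrepancy over expected loss needs its own correction and is not settled by this change.

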### SAFETY SUMMARY:

- Local tissue safety: 80mg/40mL is 2 mg/mL (which is 2000 micrograms / mL). This level was found to be safe in Rathbone/Wenke study (1). Further, the local level is expected to decrease quickly, as opposed to the sustained levels seen in tissue culture in that study.
- Systemic safety: Gentamicin/tobramycin is routinely given as a single IV dose at 4-7mg/kg (depending on severity of infection). For a 70kg patient treated with 5mg/kg dose, 350mg would be given IV (thus immediately available systemically). The dose we administer is only 80mg, a much lower dose, and is administered in the wound (thus more similar to IM than IV). Peak levels are not routinely checked at UVA for short courses of even the higher doses of IV tobramycin/gentamicin, and we find no safety issue or support for obtaining peak levels in this study. Systemic levels high enough to cause side effects are typically associated with dosing that is higher than recommended or too frequent to allow adequate renal clearance.
- In cases of renal impairment, dosing is typically spaced out further to allow time for renal clearance (see attached below from Stanford Guidelines 2013). This would not create a safety issue in our study, as a single 80mg dose is administered. If ongoing therapy with a systemic aminoglycoside is required (either gentamicin or tobramycin), the patient's primary team would be made aware of the intra-operative dose and follow serum levels as appropriate based on repeated dosing.
- This route of administration of local tobramycin represents the current standard of care in my practice. I have treated all open fractures this way since starting at UVA in 2012, and have observed no adverse effects. In fact, my impression is that the infection rate is lower as a result of this practice.

Unpublished pilot data from a single trauma surgeon at UNC Chapel Hill demonstrated a significantly lower infection rate in patients treated with local aminoglycoside (initially gentamicin, then changed to tobramycin once above Wenke data showing lower potential for local toxicity was published). In the comparison group (received no local antibiotics) the overall incidence of deep infection was 4.8% (11/243) while in the current group it was 0.6% (2/343, p=0.0025). Looking specifically at patients treated with ORIF found a historical deep infection rate of 6% (8/134) versus 1.2% (2/170, p=0.0247) in the local antibiotic group. Tibia fractures had a historical deep infection rate of 10% (3/30), and there were no infections in the local antibiotic group (0/56, p=0.0397). For open fractures, the historical group had 19% (5/26) infection rate versus none (0/34) in the local antibiotic group (p=0.012).

## Background

### 1. Provide the scientific background, rationale and relevance of this project.

Local antibiotics provide high local concentrations with lower systemic levels than parenterally administered antibiotics. The delivery of local antibiotics can both supplement and sometimes obviate the need for systemic antibiotics. In certain instances, the target area of treatment may be avascular, preventing systemic antibiotics from reaching the targeted site. In these scenarios, local antibiotics may serve as the only effective option in treating the infection. Perhaps the main advantage of local antibiotic therapy is the ability of an antibiotic to reach a high local concentration while simultaneously having a low or undetectable systemic concentration, thereby avoiding certain negative side effects such as nephrotoxicity and ototoxicity and decreasing the chances of developing pathogenic resistance.[2-4] At this high level of local concentration, many bacteria that might otherwise be normally resistant to an antibiotic fall within its spectrum of activity.[5]

Antibiotics can be effectively administered in aqueous solution, and do not necessarily require a carrier. While antibiotic (as well as antiseptic) solutions have been used for many years, there is clinical data that suggest this method of delivery is effective. A significant positive impact was shown in a series of shoulder arthroplasty patients, where the rate of infection was decreased by one order of magnitude with intra-articular injection of aqueous gentamicin performed after wound closure.[ 6] This method of administration has also been effective in a rat model, where aqueous gentamicin was significantly better for infection prophylaxis after placement of a metal implant and contamination with *Staphylococcus aureus*, and this effect was further improved by concomitant administration of systemic antibiotics.[7,8] This method of delivery is distinct from antibiotic solution for irrigation, as the aqueous antibiotic is injected into the surgery site after the wound is closed. An 18 ga needle is used adjacent to the incision to inject the solution throughout the wound. This technique allows the solution to ideally infiltrate the interstices or depths of the wound. In practice, the solution has been made in a concentration of 2 mg/mL (80 mg aminoglycoside in 40 mL injectable saline). Recent data which suggested lower local cytotoxicity with tobramycin compared to gentamicin [5] has led us to choose tobramycin in this application. We will therefore use tobramycin as the study drug in this protocol.

The advantages of delivering antibiotic in aqueous form are several, including cost, as there is no need for a specialized vehicle of delivery. The antibiotic drugs are approved and ready for use this time. Also, the wound encounters a higher maximum antibiotic concentration, potentially improving antibiotic efficacy.

Drawbacks to this method may include poor sustained antibiotic level. However, other vehicles for delivery such as collagen sponge have been shown to elute the drug very quickly, then potentially become a

foreign body at the surgical site. Thus, this method of antibiotic delivery may be more effective in a situation where sustained delivery is not required, such as prophylaxis of surgical site infections.

Regarding local toxicity and safety, Rathbone et al demonstrated levels of toxicity for many commonly used antibiotics.[ 1] This data is helpful for determining appropriate concentrations that are acceptable in the wound cavity, regardless of the delivery method. Upon evaluating osteogenic cell viability and activity as measured by alkaline phosphatase activity, wide variability was noted, even within families of antibiotics. Rifampin, tetracyclines, and ciprofloxacin were noted to be particularly cytotoxic, with considerable decrease in cell number and activity at concentrations of even 100mcg/mL. Tobramycin, vancomycin, and amikacin were noted to be least cytotoxic. Of note, cell number and activity were measured at time points of 10 and 14 days for various concentrations of each antibiotic. While the response of osteogenic cells to these concentrations of antibiotics is useful information, it should be noted that these are measured in response to sustained levels of antibiotics, and in the clinical setting the antibiotics levels are highest at early time points then often decrease rapidly.

### **Hypothesis to be Tested**

Local aqueous tobramycin used for infection prophylaxis injected into open fracture wounds following definitive closure prevent infections, and decreases re-operation rate in patients with open fractures within 6 weeks of administration.

### **Study Design: Biomedical**

#### **1. Will controls be used? Yes**

**► IF YES, explain the kind of controls to be used.**

We will use placebo controls who will receive 40 mL of 0.9% NS injected into the closed wound at the end of surgical treatment.

#### **2. What is the study design?**

Double blind

#### **3. Does the study involve a placebo? Yes**

**► IF YES, provide a justification for the use of a placebo**

This study will need placebo group to evaluate the effectiveness of local injection of tobramycin.

### **Human Participants**

**Ages:** 18-70

**Sex:** Both

**Race:** All

#### **Subjects- see below**

- 1. Provide target # of subjects (at all sites) needed to complete protocol.** 133
- 2. Describe expected rate of screen failure/ dropouts/withdrawals from all sites.**

Approximately, 20% of subjects will be lost to follow up

**3. How many subjects will be enrolled at all sites? 133**

**4. How many subjects will sign a consent form under this UVa protocol? 133**

**5. Provide an estimated time line for the study. 2 years**

### **Inclusion/Exclusion Criteria**

**1. List the criteria for inclusion**

- Ages 18 – 70 years
- Gustilo Type I,II,IIa open fracture (s)
- Ability to provide informed consent (or proxy consent in cases where subject is temporarily impaired when intubated and sedated)
- Subject should be able to follow up at the scheduled times following surgery
- Subjects who may have compartment syndrome, renal insufficiency, and those who are immunosuppressed regardless of antibiotic administration will also be included in the study
- 

**2. List the criteria for exclusion**

- Closed fracture
- Severe injury requiring flap coverage or vascular reconstruction (Gustilo-Anderson Type IIIB and C respectively)
- Aminoglycoside allergy
- Presentation greater than 48 hours after injury
- Pathologic fracture
- Preexisting infection in bone with an open fracture
- Patients with multiple trauma involving liver, kidney, or brain
- Pregnancy (self-reported)
- Current status as prisoner

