**2. What are the statistical considerations for the protocol?**

- This is a prospective, randomized double blind study. Subjects will be randomized to antibiotic (80mg tobramycin/40mL saline) or placebo arm (40mL of 0.9% saline).
- The primary objective of this study is to evaluate the efficacy of local antibiotics in decreasing incidence of infection. The primary outcome will include evidence of infection in the first 6 weeks of surgery. Infection will be defined as major and minor, with major indicated by return to the operating room for irrigation and debridement. Minor infection is represented by documentation of cellulitis or superficial infection at surgical site and administration of oral antibiotics. .
- Superficial infection as indicated by documentation of cellulitis at surgical site and administration of oral antibiotics with the indication of wound problems. The primary purpose of this study is to document infection rates in the first 6 weeks after surgery. If an infection is found, it will be cared for per standard clinical care; however, it will not be followed for research purposes.
- There will be no contingencies for early stopping as the patients are receiving a single dose of antibiotics. There will be no interim analysis or stratification factors
- We expect approximately - 60 – 65 open fractures within a year to be treated at UVA based on historical records.

We will use a one-sided test for proportions to compare the control and experimental groups for the primary endpoint (presence of infection) and the secondary endpoint of evidence of non-union. A p-value less than 0.05 will be considered a significant result.

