4. Do you plan to ask the subjects to do anything, other than answering questions, for the study prior to signing a consent? NO

**5. How will the consenting process take place with either the prospective subject, the subject's legally authorized representative or parent/legal guardian of a minor ( if applicable)?**

HIPPA:

If the individual, obtaining consent, works under the HIPAA Covered Entity consenting is covered under Health Care Operations.

If the individual obtaining consent does not work under the HIPAA covered entity, HIPAA does not apply.

Subjects who are being treated for open fractures at University of Virginia, who agree to participate in the study will be asked to sign an informed consent at the hospital. Subjects will be given ample time to go over the informed consent, and an opportunity will be provided to ask questions. Subjects are also allowed to discuss with family and relatives before they sign the consent. Anywhere, from one hour to one week may pass between written consent and initiation of study procedures.

If subject is unresponsive or intubated, and cannot adequately answer the questions and if it is determined that the patient's level of cognition is not likely to change before surgery, a legally authorized representative (LAR) will be approached for proxy consent. Guidance will be provided to assist the LAR in making consent decision. They will be advised to base the decision on the patient's expressed wishes, or, what they believe the patient would have desired under the circumstances of the injury. His or her beliefs and values. When participant regains capacity to consent during the study period, the participant will be re-consented using standard consenting procedures as described below.

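### The infection exclusion covers only bone while the primary endpoint counts cellulitis and superficial infection of any onset, so a wound already infected at entry can be scored as a failure of prophylaxis

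*Combined protocol and SAP*

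**What the plan says.** The trial tests prevention. Under Hypothesis to be Tested it states: "Local aqueous tobramycin used for infection prophylaxis injected into open fracture wounds following definitive closure prevent infections".

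Under Statistical Considerations, item 2, the endpoint is framed broadly: "The primary outcome will include evidence of infection in the first 6 weeks of surgery". It has two components. Major infection is defined "with major indicated by return to the operating room for irrigation and debridement". For the other, "Minor infection is represented by documentation of cellulitis or superficial infection at surgical site and administration of oral antibiotics". Neither component says that the infection must begin after the study injection.

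Among the exclusion criteria, the one line on existing infection is "Preexisting infection in bone with an open fracture". The only other criterion that bears on the question is a time limit, "Presentation greater than 48 hours after injury". The inclusion list expressly admits immunosuppressed subjects.

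On timing, Statistical Considerations, item 1, places randomization before surgical treatment. The consent text in Appendix: Recruitment, item 5, allows "from one hour to one week may pass between written consent and initiation of study procedures". Item 7 of that appendix adds that some wounds cannot be closed at the index operation, and the injection is given only after closure (Biomedical Research, item 1).

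**The concern.** The plan already treats infection present at entry as disqualifying, but only when it is in bone. Its endpoint is met by infection in other tissue. A subject with cellulitis or a superficial wound infection at enrolment passes every listed criterion. If that infection is documented and treated with oral antibiotics after surgery, or leads to a return to the operating room, the endpoint is met.

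An injection cannot prevent an infection that is already there. Such events fall on both arms alike and shrink the relative contrast. The design has little room for this: it plans 70% power and expects less than one event on tobramycin. Without a recorded baseline wound status, the analysis may also be unable to separate old infections from new ones.

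**Working it through.** **Does anything else close the gap?**

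- Eligibility: no inclusion or exclusion criterion names wound, skin or soft-tissue infection.
- Restricted drugs (Inclusion/Exclusion Criteria, item 3): this applies during the study and to antibiotics unrelated to the fracture. It is not an entry rule.
- Baseline procedures (Biomedical Research, item 2): medical record review only; no wound check is required.
- The 48-hour limit: it governs presentation, not the time of randomization or injection.
- Endpoint: there is no new-onset condition, so the mismatch holds whichever date starts the 6-week window.

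Nothing closes it.

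**Reproducing the plan's figure.** Inputs from Statistical Considerations, item 3: 10% versus 1%, one-sided alpha 0.05, power 70%, 60 per group. The plan does not name the variant of the test. The pooled-variance normal formula without continuity correction gives, with p̄ = (p_c + p_t)/2,

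power = Φ{ [ (p_c − p_t)√n − 1.645·√(2p̄(1−p̄)) ] / √(p_c(1−p_c) + p_t(1−p_t)) }

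For n = 60 and p̄ = 0.055: (0.09 × 7.746 − 1.645 × 0.3224) / 0.3161 = 0.528, and Φ(0.528) = 0.701. Solving for 70% power gives 59.8, so 60 per arm. The plan's figure reproduces.

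**Adding subjects infected at entry.** The documents give no share f, so a range is assumed. Every such subject counts as an event in either arm, and all others follow the planned rates:

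p_c = f + (1 − f)·0.10 and p_t = f + (1 − f)·0.01

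| f | Expected infected at entry, of 120 | p_c | p_t | Power at 60 per arm | Risk ratio |
|---|---|---|---|---|---|
| 0 | 0 | 10.0% | 1.0% | 70.1% | 0.10 |
| 0.5% | 0.6 | 10.45% | 1.5% | 66.7% | 0.14 |
| 1% | 1.2 | 10.9% | 2.0% | 63.6% | 0.18 |
| 2% | 2.4 | 11.8% | 3.0% | 58.1% | 0.25 |

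**If only half of them meet the endpoint**, p_c = f/2 + (1 − f)·0.10 and p_t = f/2 + (1 − f)·0.01. For f = 1% this is 10.4% versus 1.49%, power 66.5%. For f = 2% it is 10.8% versus 1.98%, power 63.2%.

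**Sensitivity to single cases.** Expected events are 60 × 0.10 = 6 and 60 × 0.01 = 0.6. Take 6 versus 1 as the nearby whole-number result and use z = [(a − b)/60] / √(2q(1−q)/60), with q = (a + b)/120:

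- 6 versus 1: z = 1.95, one-sided p = 0.026
- one case added to each arm, 7 versus 2: z = 1.73, p = 0.042
- two added to each arm, 8 versus 3: z = 1.58, p = 0.057
- one added by chance to tobramycin only, 6 versus 2: z = 1.46, p = 0.072

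**The case against.** The best defence is that the affected group is small. Presentation after 48 hours is excluded, and Appendix: Recruitment, item 7, calls open fractures surgical emergencies to be treated as quickly as possible. Its account of delay (resuscitation, staged closure) does not suggest that wounds are left untreated. This stands: such cases should be uncommon. A 5% share would cut power to 46.0%, but it would need 6 of 120 wounds infected at entry, and nothing in the documents supports that.

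Not every such subject would count, either. The minor component needs both documentation at the surgical site and oral antibiotics, and these subjects also receive surgery and systemic antibiotics. This stands too, so the table shows the largest loss for each assumed share under its model. The plan also draws its rates from historical data without saying whether infected wounds were left out. If both rates already include them, there is no loss beyond the planned 70%.

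A reader might go further and infer that one or two such subjects would make an effective drug look ineffective, since they can double or triple the tobramycin rate. That is too strong. Two among 120 (f = 1.7%) give 11.5% versus 2.65%, still a 77% relative reduction (1 − 2.65/11.5), with power 59.8%. The proportional jump looks large only because 0.6 events are planned.

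None of this removes the mismatch. The eligibility text admits these subjects, the endpoint can count them, and no rule says otherwise.

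**Conclusion.** The point holds as a mismatch between the eligibility rule and the endpoint, and it should be corrected. For an assumed 0.5% to 2% infected at entry, all counted as events, power at 60 per arm falls from 70% to between about 67% and 58%. It falls less if only some count. Because so few events are expected, one or two cases can move a result across the 0.05 line.

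This rests on an assumed share, on the planned 10% and 1% applying to everyone else, and on the pooled one-sided test that reproduces the plan's 60 per group.

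Two further inferences are not supported. The first is systematic bias: randomization balances these cases on average, so the expected effect is dilution, with nothing that favours tobramycin. The second is an error in the sample-size calculation: 60 per group is correct for its stated inputs.

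**What to change.** 1. **Exclusion criteria.** Replace the bone-only line with: *Preexisting infection in bone or soft tissue (including cellulitis) at the open fracture site before randomization.*
2. **Data collection.** Record wound infection status at screening and again at the first study injection. The second record is needed because randomization precedes surgery and closure may be delayed, so an exclusion at randomization cannot catch infection that arises in between.
3. **Endpoint** (Statistical Considerations, item 2). State that the primary endpoint counts infection not already documented before the first study injection. Status at that time precedes any study treatment, so the rule does not depend on the arm.
4. **Analysis.** Keep all randomized subjects in the primary analysis. Add a sensitivity analysis that leaves out those infected before injection.
5. **Outside sites.** Changing this protocol's criteria does not change eligibility at sites that UVA says it will not oversee, yet their data will be combined. Request the same item from them; infection information is already among the data to be received (Information from Outside Institution, item 2). The endpoint rule and sensitivity analysis can then be applied to the pooled data.

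The cost is a few ineligible subjects, one or two data fields, a sentence in the endpoint definition and agreement with the other sites on one item. The planned sample size does not change.
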